5.5 Prior and Concomitant Medications and Procedures

Medications:

All medications will be coded using the current version of the World Health Organization Drug (WHO Drug) dictionary [Mar2021 B3].

Prior medications will be defined as all medications taken before the first dose of study drug with a stop date prior to the first dose of study drug.

Concomitant medications will be defined as all medications with a start date before, on or after the first dose of study drug and with a stop date on or after the first dose of study drug or with a missing stop date.

Prior and concomitant medication will be summarised by number and percentage of subjects by treatment group as defined in Table 5- on ITT and PPS. The summary tables will be sorted by decreasing frequency of overall subjects receiving VIT-2763 and decreasing frequency of drug or procedure name in a given drug class (therapeutic subgroup [2nd level of the anatomical therapeutic chemical (ATC) classification], chemical subgroup [4th level of the ATC classification] and Preferred Name). In case of equal frequency regarding drug or procedure class, alphabetical order will be used. A same medication or procedure during the study for one subject will be counted once.

A listing with all prior and concomitant medications will be provided including the flag for prior or concomitant on Enrolled population.

Procedures:

Prior procedures will be defined as all procedures performed before the first dose of study drug with a stop date prior to the first dose of study drug.

Concomitant procedures will be defined as all procedures with a stop date on or after the first dose of study drug or with a missing stop date.

All procedures will be coded using the MedDRA 24.0.

A listing with all prior and concomitant procedures will be provided including the flag for prior or concomitant on Enrolled population. Procedures will not be tabulated.

5.6 Study Drug Exposure and Compliance

The following durations of study drugs (including VIT-2763 and Placebo) will be computed in days:

Duration of study drug (in days) = Treatment stop date – Treatment start date + 1

Treatment start and stop dates will be derived as defined in Section 5.1.4.

The total amount of VIT-2763 taken in mg will be calculated for each subject from the difference between the amount of VIT-2763 dispensed in mg and the amount of VIT-2763 returned in mg. It will be compared to the amount expected to be taken for subjects randomised in a VIT-2763 cohort to calculate the percentage compliance to VIT-2763. Derivation details are provided below.

Total amount of VIT-2763 (mg) = $30 * (\text{Number of VIT-2763 30 mg capsules dispensed} - \text{Number of VIT-2763 30 mg capsules returned}) + 60 * (\text{Number of VIT-2763 60 mg capsules dispensed} - \text{Number of VIT-2763 60 mg capsules returned})$.

The total amount of VIT-2763 taken will be computed for all randomised subjects and will be equal to 0 if no dispensation error occurred in Placebo cohort. In case of miss allocation for a patient receiving VIT-2763 instead of Placebo, the amount will be counted for VIT-2763.

Expected amount of VIT-2763 (mg) for cohort 1 = $120 * (\text{Duration of study drug in days} - 1) + 60$.

Expected amount of VIT-2763 (mg) for cohort 2 = $240 * (\text{Duration of study drug in days} - 1) + 120$.

Expected amount of VIT-2763 (mg) for cohort 3 = $360 * (\text{Duration of study drug in days} - 1) + 120$.

VIT-2763 compliance (%) = $(\text{Total amount of VIT-2763 (mg)} / \text{Expected amount of VIT-2763 (mg)}) \text{ for cohort 1-2-3} * 100$.

The total number of capsules of study drug (VIT-2763 or Placebo) taken will be calculated for each subject from the difference between the total number of capsules dispensed and the total number of capsules returned. It will be compared to the expected number of capsules to be taken by subject to calculate the percentage compliance to study drug.

Total amount of study drug (number of capsules) = Number of capsules dispensed - Number of capsules returned

Expected amount of study drug (number of capsules) for cohorts 1, 2, 4a = $4 * (\text{Duration of study drug in days} - 1) + 2$

Expected amount of study drug (number of capsules) for cohort 3, 4b = $6 * (\text{Duration of study drug in days} - 1) + 2$

Study drug compliance (%) = $(\text{Total number of capsules taken} / \text{Expected number of capsules taken}) * 100$

Duration of study drug, total and expected amount of VIT-2763 and total and expected amount of study drug in terms of number of capsules taken will be summarised using standard descriptive statistics for continuous variables on the ITT population and the PPS if they differ.

The calculated percentages of compliance will be categorized as:

- < 80% compliance
- $\geq 80\%$ to $\leq 110\%$ compliance
- $> 110\%$ compliance

Compliances for VIT-2763 and for study drug will be summarized for the ITT population and the PPS if they differ as follows:

- Percent compliance presented by default summary statistics for continuous variables.
- Number and percentage of subjects within each of the compliance categories.

The number and percentage of subjects who had at least one incidence of a change/interruption to their dosing will be summarised along with reasons of dose change/interruption for the ITT population and the PPS if they differ.

A listing of exposure data will also be presented together with compliance on ITT.

5.7 Efficacy Analyses

5.7.1 Primary Efficacy Analysis

The changes in indirect bilirubin from baseline to Visit 6 (after 8 weeks of treatment) will be summarised using standard descriptive statistics for continuous variables with 95% confidence interval (CI) of the mean on the ITT population by randomised treatment groups as described in Table 5.

Analysis visit windows will be considered for the primary efficacy analysis (see Section 5.1.2). The analysis will be repeated on the PPS by actual treatment group and on mITT if applicable.

Three sensitivity analyses will be run on the ITT population as the primary analysis, with the imputation of the missing data due to haemolised samples at baseline or Visit 6 (see section 5.1.9). Analyses will be:

- Imputation of missing baseline with the median of the non-missing baseline of the pooled subjects. Imputation of Visit 6 missing data using the minimal value within the same cohort.
- Imputation of missing baseline with the median of the non-missing baseline of the pooled subjects. Imputation of Visit 6 missing data using mean value within the same cohort.
- Imputation of missing baseline with the median of the non-missing baseline of the pooled subjects. Imputation of Visit 6 missing data using maximum value within the same cohort.

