2.2 Study Design Rationale

This is a randomised, double-blind, placebo-controlled, parallel group trial that explores 3 different dosing regimens of VIT-2763: 60 mg BID, 120 mg BID and 120 mg TID.

The treatment duration of 8 weeks is considered sufficiently long enough to explore the effects of VIT-2763 on markers of haemolysis, haematological indices, and vascular inflammation, safety and tolerability, iron and erythropoiesis related blood parameters, pain

and quality of life, and at the same time to discern possible negative effects on iron restriction over time.

Subjects in this study will be required to have experienced at least 1 and no more than 10 VOC episodes reported within 12 months prior to screening, in order to define a symptomatic disease status, but to exclude the most severely impacted subjects, e.g., those who suffer from additional comorbidities. There is no commonly agreed threshold in the number of VOC episodes experienced in patients with SCD. A study including more than 8,500 patients with a follow-up period of 2.7 years evaluated the prevalence rate of VOC episodes (uncomplicated and complicated VOC episodes), and the primary reasons for emergency room visits and in-patient admissions for SCD patients [19]. During the first-year follow-up period, an average of 2.79 VOC episodes were identified per SCD patients, with 1.06 VOC episodes treated in the in-patient setting and 0.90 VOC episodes treated in the emergency room without admission. The defined baseline characteristic of having experienced at least 1 to no more than 10 VOC episodes ensures that subjects are sufficiently stable, while this threshold is in line with the overall prevalence of VOC episodes in the target population and compares well with the baseline characteristics of SCD patients in similar early clinical trials conducted in the past [20]. Hence, the likelihood that subjects will suffer from VOC episodes during the 8-week treatment schedule while participating in the main trial is considered low.

Patients with homozygous HbS/S and the compound heterozygous condition HbS/ β T0 thalassaemia present amongst the most prevalent SCD genotypes and are clinically very similar [21].

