12. STATISTICAL ANALYSIS

12.1 Statistical Methods

All statistical analyses will be performed using SAS Version 9.4 or later (SAS Institute Inc. SAS/STAT, Cary, NC). The detailed methodology for summary and statistical analyses of the data collected in this trial will be documented in a SAP that will be finalised prior to database lock and the unblinding of the study.

For continuous parameters, summary statistics will include the number of subjects, mean, standard deviation, quartiles, minimum and maximum, and the 95% confidence interval of the mean (if appropriate). For categorical parameters, summary statistics will include counts, percentages, and the 95% confidence interval of the percentages (if appropriate) in each category.

Summary statistics will be provided on overall subjects receiving VIT-2763, by dose and for all subjects receiving placebo. Subjects from Cohort 4a and Cohort 4b will be combined into 1 placebo group.

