12.8 Primary and Secondary Efficacy Evaluations

The changes in haemolysis markers from baseline to Visit V6 (after 8 weeks of treatment) will be summarised on overall subjects receiving VIT-2763, by dose group and on all subjects receiving placebo.

The ITT population will be used for the analysis of the primary and secondary endpoints related to haemolysis markers. These analyses will also be repeated on the PPS.

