5.1.5 Tables and Listings Presentation

For all analyses, summary statistics will be tabulated for the 5 following treatment groups as presented in Table 5 and corresponding to the 3 VIT-2763 cohorts, the pooling of the 2 placebo cohorts and the pooling of all VIT-2763 subjects.

Table 5 Treatment groups labels

Treatment Groups Labels	Treatment Groups Short Labels	Table order¹
Cohort 1: VIT-2763 60 mg BID	VIT-2763 60 mg BID	1
Cohort 2: VIT-2763 120 mg BID	VIT-2763 120 mg BID	2
Cohort 3: VIT-2763 120 mg TID	VIT-2763 120 mg TID	3
Cohorts 1-2-3: All VIT-2763	All VIT-2763	4
Cohort 4a/4b: Placebo	Placebo	5

¹ From left to right in statistical tables

Shorts labels will be used in tables while entire labels will be used in listings and figures for both randomized and actual treatment arms.

The listings will display all the data contained in the CRF, including the screen failure patients collected information if appropriate. The listings will be ordered by dose (from lowest to highest) and for all subjects receiving placebo (Cohorts 4a and 4b combined) and subject number.

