5.7.2 Secondary Efficacy Analysis

Summaries of change from baseline values will be reported at Visit 6 (after 8 weeks of treatment) for direct and total bilirubin, LDH, potassium, Hb and free haptoglobin using standard descriptive statistics for continuous variables with 95% CI of the mean by randomised treatment groups as described in Table 5 on the ITT population.

The analysis will be repeated on the PPS as well by actual treatment group and on mITT if applicable.

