5.7.3 Exploratory Efficacy Analysis

Summaries of values and changes from baseline for each haemolysis marker (indirect, direct and total bilirubin, LDH, potassium, Hb and free haptoglobin) will be reported for each visit using standard descriptive statistics for continuous variables on the ITT population by randomised treatment groups as described in Table 5. Analyses will be repeated on the PPS by actual treatment group and on mITT if applicable.

Summaries of absolute and percent changes from baseline for indirect bilirubin, CHCM and MCHC will also be reported for each visit using the same approach.

Number and percentage of subjects who had at least 20% reduction in Indirect Bilirubin from baseline will be summarized at each post-baseline visit.

Number and percentage of subjects who had at least 5% reduction in CHCM and MCHC from baseline will be summarized at each post-baseline visit.

Analyses will be repeated on the PPS by actual treatment group and on mITT if applicable.

For each haemolysis marker, 3 figures will be provided:

- Line plots by subject: individual marker values (y-axis) in function of target visit day (x-axis) joined by subject and plotted in separate windows for the randomised cohorts (1, 2, 3, 4).
- Line plots by subject in log scale: same plot as previous with individual marker values displayed in a \log_{10} scale (y-axis)
- Means with 95% CIs of changes from baseline marker values for the 4 randomised cohorts (y-axis) in function of target visit day (x-axis). Means will be joined by group.

All graphics will be done on the ITT.

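### The efficacy analyses give a confidence interval for each arm's mean change but none for the difference from placebo

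*SAP*

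**What the plan says.** SAP 5.7.1 states that changes in indirect bilirubin from baseline to Visit 6 "will be summarised using standard descriptive statistics for continuous variables with 95% confidence interval (CI) of the mean on the ITT population". SAP 5.7.2 treats direct and total bilirubin, LDH, potassium, Hb and free haptoglobin alike, "using standard descriptive statistics for continuous variables with 95% CI of the mean by randomised treatment groups".

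The columns come from Table 5 in SAP 5.1.5: the three dose cohorts plus "the pooling of the 2 placebo cohorts and the pooling of all VIT-2763 subjects". SAP 5.1.1 lists the standard descriptive statistics, and all are one-sample quantities (number, mean, SD, median, minimum, maximum).

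SAP 5.7.3 adds by-visit summaries, responder counts and, for each haemolysis marker, a figure showing "Means with 95% CIs of changes from baseline marker values for the 4 randomised cohorts". The three sensitivity analyses in SAP 5.7.1 change only how missing values are filled, for example "Imputation of Visit 6 missing data using mean value within the same cohort".

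The protocol is no different. Section 12.1 says "Summary statistics will be provided on overall subjects receiving VIT-2763, by dose and for all subjects receiving placebo", and section 12.8 says that changes in haemolysis markers "will be summarised on overall subjects receiving VIT-2763, by dose group and on all subjects receiving placebo".

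SAP 3.1 and 3.2 define no hypothesis test and no decision rule, and call the analyses descriptive.

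**The concern.** Protocol 2.2 describes the design: "This is a randomised, double-blind, placebo-controlled, parallel group trial that explores 3 different dosing regimens of VIT-2763". The primary objective (Protocol 3.1, SAP 2.1.1) is to explore what VIT-2763 does to haemolysis markers. In such a design, the drug's effect is the difference in change between an active arm and placebo. The planned output estimates the change in each arm separately.

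A within-arm change mixes the drug effect with anything that moves every arm, such as regression to the mean after selection at screening or natural fluctuation. The documents expect such movement: Protocol 2.2 and SAP 1.1 give the natural variability of haemolysis markers as one reason for having placebo subjects.

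The layout also sets a column of 18 active subjects beside a column of 6 on placebo. The first interval is much narrower, so it can exclude zero while the placebo interval does not, even when both arms changed by the same amount. A reader could take that pattern for a drug effect.

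**Working it through.** The documents give no sample-size, power or SD figure to reproduce. Widths are therefore in units of the SD of change, assuming normal data and equal SDs.

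**Inputs**
- 24 subjects randomised 3:3:3:2:1 (SAP 2.5). 24 × (3, 3, 3, 2, 1)/12 = 6, 6, 6, 4, 2, so 18 active and 4 + 2 = 6 pooled placebo.
- Replacement floor of 5 evaluable subjects per arm (SAP 2.5). Four per arm is an assumption, to show the effect of missing Visit 6 values.

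**Formulas for 95% half-widths**
- Within an arm: t(0.975, n−1)/√n.
- Difference, with variance pooled over four arms: t(0.975, N−4) × √(1/n₁ + 1/n₂).

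**Results with 24 complete**
- One dose, within arm: t(5 df)/√6 = 1.049.
- All VIT-2763, within group: t(17 df)/√18 = 0.497.
- One dose minus placebo: t(20 df) × √(2/6) = 1.204.
- All VIT-2763 minus placebo: t(20 df) × √(1/18 + 1/6) = 0.983.
- Ratio for the pooled column: 0.497/0.983 = 0.51.

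| Complete per arm | df | Dose minus placebo | All VIT-2763 minus placebo |
|---|---|---|---|
| 6 | 20 | 1.20 | 0.98 |
| 5 | 16 | 1.34 | 1.09 |
| 4 | 12 | 1.54 | 1.26 |

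**How often the columns would mislead.** Simulation with no drug effect, four arms of 6 and 200,000 runs. The event is that the active interval excludes zero and the placebo interval does not. The drift common to all arms is assumed.

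| Assumed drift (SD) | All VIT-2763, not placebo | One dose, not placebo |
|---|---|---|
| 0 | 5% | 5% |
| 0.1 | 7% | 5% |
| 0.25 | 16% | 7% |
| 0.5 | 43% | 14% |
| 0.75 | 58% | 22% |

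The difference from placebo excludes zero in about 5% of runs at every drift.

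**Baseline adjustment.** Mean half-width for one dose minus placebo, in baseline-SD units, at assumed baseline to Week 8 correlations (20,000 runs):
- 0.3: 1.408 to 1.169, 17% narrower.
- 0.5: 1.190 to 1.061, 11% narrower.
- 0.7: 0.920 to 0.873, 5% narrower.
- 0.9: 0.532 to 0.534, no gain.

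Dividing by the SD of change, √(2(1−ρ)), gives 1.169/1.183 = 0.99, 1.061/1.000 = 1.06 and 0.873/0.775 = 1.13 SD of change at 0.3, 0.5 and 0.7.

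**Intervals after single imputation.** The adjusted model was simulated with 6 per arm, correlations of 0.3 to 0.7 and an assumed number of missing Visit 6 values (6,000 runs per setting). With observed cases and values missing at random, the interval wrongly excludes zero in 5%. With one value per arm imputed, the rate is 5–7% (minimum or maximum) and 10–11% (mean). With two per arm, it is 12–13% and 20–21%.

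**Multiplicity.** 7 markers × 4 contrasts = 28 intervals. With no drug effect, at least one excludes zero in 61%, 49% and 34% of runs at assumed between-marker correlations of 0, 0.5 and 0.8 (unadjusted contrasts, 20,000 runs). For the four indirect bilirubin contrasts alone the figure is about 13%.

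**The case against.** The strongest reply is that the plan is consistent with itself. The endpoint is a mean change, SAP 5.7.1 estimates that mean change, and the trial openly has no hypothesis, decision rule or sample-size calculation. Placebo is there to separate side effects and show natural variability, which a placebo column does. That column stands beside every active column, with n, mean and SD, so a reader can work out an unadjusted difference. The high misreading rates need a drift that no document supports and a reading rule that the SAP never adopts. With no drift, the rate in the direction of benefit alone is 2.4%.

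Part of this stands. The planned tables contain no error, the drift figures are conditional, and the width argument concerns mainly the pooled column. But a descriptive trial has reason to omit tests, not estimates. The SAP already reports 95% intervals and attaches them to arm means. A hand-made difference would not be pre-specified or baseline-adjusted, and the choice of contrast and variance would be left until after unblinding. Showing natural variability in placebo subjects is useful precisely because it allows a comparison.

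Several objections to the remedy are fair but do not defeat it:
- The proposed model omits genotype, the stratification factor.
- SAP 5.1.9 does not regard withdrawals as missing at random. An observed-case model shares that limit with the planned primary analysis.
- An equal-weight average of doses will not match the pooled column exactly if missingness is unequal.
- Repeating the model on the per-protocol set and any modified ITT set would multiply the intervals.

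**Conclusion.** The concern holds. No passage in either document plans a difference from placebo, or an interval for one, for any efficacy endpoint, although the randomised design and the primary objective call for it. The all VIT-2763 column is where it matters most: its interval is about half as wide as that of the comparison it may be taken to represent. For single doses the main loss is that the effect itself is never stated.

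The widths assume normal data, equal SDs and complete arms. The misreading rates also rest on an assumed drift and are about 5% without it. This is an inexpensive addition that should be made.

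**What to change.** Keep every planned table. Before unblinding, add to SAP 5.7.1 and 5.7.2, for each haemolysis marker:

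- A linear model of Week 8 change on cohort (three doses, pooled placebo) and baseline value, fitted to subjects with observed baseline and Visit 6 values.
- The difference from pooled placebo for each dose, and for all VIT-2763 as the equal-weight average of the three doses, with 95% CIs and no p-values.
- A label saying that these are exploratory and not adjusted for multiplicity.
- Under the three single-imputation analyses of indirect bilirubin, the point estimate of the difference only, because ordinary intervals there treat filled-in values as observed.

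The documents do not give the unblinding date. If the blind is already broken, report the same model as post hoc. Protocol 12.1 leaves detailed methods to the SAP and SAP section 1 gives the SAP precedence, so SAP wording appears to be enough.

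The cost is one model per marker on data already collected. The downsides are 1 df for baseline, about 28 unadjusted intervals and wide limits. With 24 complete these are 1.2 SD per dose and 1.0 SD for all VIT-2763 before baseline adjustment, and roughly 1.0 to 1.1 SD per dose after it at correlations of 0.3 to 0.7. The equal-variance assumption also cannot be checked well: with 5 df, the 95% limits for an SD run from 0.62 to 2.45 times its estimate.

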A required Hb threshold between 6.0 g/dl and 10.4 g/dl for female and >11.0 g/dl for male subjects at the time of screening is considered appropriate, as it typically covers most patients with HbS/ β T0 thalassaemia and HbS/S genotype. In addition, ineffective erythropoiesis is expected to be more pronounced in HbS/ β T0 because of the beta-thalassaemia genotype.

Subjects with absolute reticulocyte count or % reticulocyte count >1.5 \times ULN during screening are eligible. The reticulocyte count is useful as a marker to estimate the degree of erythropoiesis and the appropriateness of the bone marrow response to anaemia. Absence of reticulocytosis in anaemia usually signals a problem with the bone marrow such as an aplastic anaemia, and points to a lower impact on ineffective erythropoiesis. The reticulocyte count is reported to be elevated between 4 to 15% in samples from SCD patients [11,22-24]; however, a threshold of 1.5 \times ULN seems plausible in this trial to target those patients who might respond best following VIT-2763 administration.

VIT-2763 lowered serum iron in rodents, dogs, and humans (healthy volunteers and non-transfusion dependent beta-thalassaemia patients) suggesting similar mechanism of action of VIT-2763 in these species [15,16] (see IND, Section 1.11.4). The PD effect of VIT-2763 in humans can be monitored by determination of plasma iron levels (acute effect) and haematological RBC indices (chronic effect). In addition, biomarkers for haemolysis,

inflammation and haemopoietic/erythropoietic activity in SCD patients will be assessed as preliminary efficacy readouts. Data from the completed first-in-human study [16] revealed that oral administration of VIT-2763 to healthy male and female volunteers for up to 7 consecutive days, QD or BID dosing, and at up to 240 mg total daily dose was well tolerated with no safety findings of clinical relevance. Short-term treatment in adult subjects was well tolerated with no difference between active dose groups and placebo both in terms of frequency and intensity of AEs following single and multiple doses. The human PK profile exhibited dose linearity and only slight dose super-proportionality for C_{max} and AUC at steady-state PK.

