2.4 Sample Size Determination

This is an exploratory Phase 2a study of VIT-2763 in SCD subjects, therefore no formal sample size calculations have been conducted.

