2.5 Randomisation and Blinding

Upon completion of the baseline visit procedures/assessments, it is planned to randomise 24 subjects in a 3:3:3:2:1 ratio into 3 VIT-2763 dose groups and 2 placebo groups.

For randomisation IWRS will be used, a validated centralised procedure that automates the random assignment of treatment groups to randomisation numbers. Stratified randomisation (balanced allocation across treatment groups) will be used according to genotype (HbS/S - HbS/βT0).

Subjects eligible for randomisation will receive a randomisation number. Randomised subjects who terminate their study participation for any reason regardless of whether the IMP was taken or not, will retain their randomisation number. The next subject will be given the next randomisation number. A subject can only be randomised once. Randomised subjects who withdraw consent for further follow-up cannot be re-screened. Re-screening may be considered at the discretion of the Investigator and in consultation with the sponsor at a later point for subjects who fail to meet the protocol eligibility criteria. In such a case, the re-screened subject will be allocated a new screening number.

If more than 1 subject in any dose cohort withdraws or drops out between signing informed consent and the V6 visit, the subject will be replaced with a number randomization number until at least 5 subjects, with no major protocol deviation impacting the primary objective of the trial, per treatment/placebo (Cohorts 4a and 4b combined) arm have passed Visit V6. Subjects included to replace subjects who withdraw or drop out or with major protocol deviations impacting the primary objective of the trial, will be assigned to the same cohort as the subjects they are replacing.

The randomisation schedules, as described in Biostatistics Addendum Subject Randomisation List (BA-S) V2.0 dated 16 March 2022, will be generated and maintained by ALMAC Clinical Technologies. The schedule and the seed will be sequestered until the study database is locked and the study is unblinded. Data will also be unblinded for closed sessions of DSMB meetings.

2.5.1 *Interim Analysis*

No interim analysis is planned.

2.5.2 *Data and Safety Monitoring Board*

An independent Data and Safety Monitoring Committee (DSMB) will oversee the safety and conduct of the trial on an ongoing basis. The DSMB will be comprised of medical and statistical representatives. The DSMB members will be unblinded.

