2.6 Study Endpoints

2.6.1 Primary Endpoint

- Mean change from baseline in haemolysis markers as measured by reduction of indirect bilirubin after 8 weeks of treatment.

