3 HYPOTHESES AND DECISION RULES

3.1 Statistical Hypotheses

Due to the exploratory nature of this trial, no formal power calculations will be performed and therefore no statistical hypothesis testing has been defined.

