3.2 Statistical Decision Rules

There is no formal statistical decision rule for this study, and all analyses are considered descriptive.

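### With about 6 subjects per arm, the planned raw mean changes in indirect bilirubin carry part of any chance baseline imbalance into the cohort comparison; a supportive baseline-adjusted estimate should be added

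*SAP*

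**What the plan says.** The primary endpoint (SAP 2.6.1) is "Mean change from baseline in haemolysis markers as measured by reduction of indirect bilirubin after 8 weeks of treatment". SAP 5.7.1 reports it as a mean change, "summarised using standard descriptive statistics for continuous variables with 95% confidence interval (CI) of the mean on the ITT population", for the groups in SAP Table 5: three dose cohorts, all VIT-2763 subjects together, and pooled placebo. SAP 5.7.2 treats the secondary haemolysis markers in the same way. Neither section contains a model or covariate, so each CI rests on its own group's SD.

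The sample size is small: "it is planned to randomise 24 subjects in a 3:3:3:2:1 ratio into 3 VIT-2763 dose groups and 2 placebo groups" (SAP 2.5), and the two placebo groups are combined.

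On genotype, SAP 2.5 states "Stratified randomisation (balanced allocation across treatment groups) will be used according to genotype". It is then tabulated as a baseline characteristic (SAP 5.3) and used in no efficacy analysis.

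The SAP is open about its purpose: "There is no formal statistical decision rule for this study, and all analyses are considered descriptive" (SAP 3.2). SAP 5.7.3 also tabulates marker values by visit, draws individual line plots by cohort, and plots mean changes with 95% CIs for the four cohorts.

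**The concern.** The four cohorts will be read side by side. Protocol 2.3.3 says that the regimens are there to compare sustained with more fluctuating iron restriction. Protocol 2.2 gives placebo the role of showing the natural variability of haemolysis markers.

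A cohort that starts high by chance tends to fall more than one that starts low, whatever the drug does. In arms of 6, such imbalances are common, and part of an apparent dose pattern in the primary marker could come from regression to the mean. The planned tables would let a reader see an unequal start but would not say how much of the change it explains.

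**Working it through.** **Inputs.** From the documents: 24 subjects at 3:3:3:2:1, which is 6, 6, 6, 4 and 2. With placebo pooled (4 + 2) this gives four arms of 6. The documents give no SD, effect size or r, and no sample-size figure to reproduce (SAP 2.4: "therefore no formal sample size calculations have been conducted"). Assumed: equal SDs at baseline and Visit 6, results in baseline-SD units, and r = 0.5, 0.7 or 0.9.

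**Step 1: how large a chance imbalance is.** The SD of a baseline difference between two arms is √(1/6 + 1/6) = 0.577. The chance that two given arms differ by more than 0.5 SD is 2[1 − Φ(0.5/0.577)] = 39%. By more than 1 SD it is 2[1 − Φ(1/0.577)] = 8%.

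**Step 2: how much reaches the mean change.** Given the baselines, the expected difference in mean change under no drug effect is −(1 − r) times the baseline difference. The last column divides the shift by the standard error of the difference in mean change, 0.577 × √(2(1 − r)).

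| r | Shift from a 0.577 SD imbalance | SE of the difference | Ratio |
|---|---|---|---|
| 0.5 | 0.5 × 0.577 = 0.29 | 0.58 | 0.50 |
| 0.7 | 0.3 × 0.577 = 0.17 | 0.45 | 0.39 |
| 0.9 | 0.1 × 0.577 = 0.06 | 0.26 | 0.22 |

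In 4,000 simulated null trials of four arms of 6, the slope of the change difference on the baseline difference was −0.49, −0.28 and −0.10 unadjusted. It was within about 0.02 of zero after adjustment.

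**Step 3: what adjustment does to precision.** The SD of change is √(2(1 − r)) and the residual SD given baseline is √(1 − r²). Their ratio √((1 + r)/2) is 0.866, 0.922 and 0.975, so baseline alone cuts the SD by 13%, 8% and 3%. The half-width for an arm of 6 is t × SD/√6, with t = 2.571 (5 df, own arm), 2.086 (20 df, pooled) or 2.093 (19 df, pooled with baseline).

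| r | Formula: own arm / pooled / adjusted | Simulated mean: own arm / pooled / adjusted |
|---|---|---|
| 0.5 | 1.049 / 0.852 / 0.740 | 1.003 / 0.841 / 0.746 |
| 0.7 | 0.813 / 0.660 / 0.610 | 0.771 / 0.650 / 0.613 |
| 0.9 | 0.469 / 0.381 / 0.372 | 0.447 / 0.375 / 0.374 |

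From own-arm to adjusted, the simulated reduction is 26%, 20% and 16%; a separate run of 6,000 trials gave 25%, 20% and 16%. Pooling alone gives 1 − 2.086/2.571 = 19% by formula, or about 16% of the simulated mean width (for example 1 − 0.841/1.003). Baseline then takes a further 11%, 6% and under 1% off the simulated width (for example 1 − 0.746/0.841 = 11%).

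The adjusted CI was wider than the own-arm CI in 20%, 26% and 28% of trials. The SD of a two-arm contrast fell from 0.565 to 0.504, from 0.435 to 0.419, and from 0.263 to 0.262. For All VIT-2763 (n = 18) at r = 0.7, the formula half-width goes from 0.385 to 0.352.

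**Step 4: missing values.** SAP 5.1.9 reports more than a trivial number of missing indirect bilirubin values at baseline and Visit 6, so fewer than 24 subjects will have both. If an arm drops from 6 to 4 evaluable subjects, the own-arm half-width rises from 2.571/√6 = 1.05 to 3.182/√4 = 1.59 times the SD of change. With 4 of 24 baselines assumed missing and median-imputed, adjusted CIs were about 23%, 19% and 13% narrower than own-arm CIs.

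**Step 5: adding genotype.** With 2 of 24 subjects assumed in the smaller stratum and no genotype effect, the term widened the simulated CIs by about 2% for an arm mean (0.746 to 0.759 at r = 0.5). For a difference from placebo it widened them by about 3% (1.061 to 1.092).

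**The case against.** The best defence is that the plan promises nothing more. It states that "no formal power calculations will be performed and therefore no statistical hypothesis testing has been defined" (SAP 3.1), follows Protocol 12.8, and displays baseline values beside the changes. Under randomisation the raw mean change is unbiased on average, and chance imbalance is already part of its sampling error: at most half a standard error in Step 2. Own-arm SDs avoid assuming equal variance across doses, which is defensible in a dose-exploring study. At r = 0.9 the gain is close to nil. All of this stands, and it limits the weight of the point. It does not remove the point, because showing an imbalance is not correcting for it, and an adjusted mean with a CI is equally descriptive.

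A reader might infer three stronger things, none of which the documents support:

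- **That every planned CI is too wide because baseline is left out.** The narrowing is an average, and pooling, which needs no covariate, supplies most of it. The All VIT-2763 column has 18 subjects, not 6.
- **That genotype must be in the model because it stratifies randomisation.** Protocol 2.2 says "ineffective erythropoiesis is expected to be more pronounced in" HbS/βT0, but that concerns erythropoiesis, not change in bilirubin. The same section describes the two genotypes as clinically close. No split is given, and allocation is already balanced on genotype.
- **That a full set of 24 baselines is available.** Sampling is scheduled for everyone, but SAP 5.1.9 reports missing values.

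**Conclusion.** The point holds as a limitation of the primary readout. Raw mean changes in arms of about 6 pass on (1 − r) of any chance baseline imbalance. For an imbalance of one standard deviation of its chance distribution, that is 0.06 to 0.29 baseline SDs over the assumed range of r. The planned summaries are not invalid, and no test or decision rule rests on them.

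The sizes assume equal SDs at both visits, normal data, no true treatment effect, and complete arms of 6 except where stated. The adjustment removes differences between cohorts at the start; it does not remove a shift common to all arms.

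**What to change.** Keep the descriptive tables. Add to SAP 5.7.1, and for the corresponding markers to 5.7.2, one supportive and descriptive linear model of Visit 6 change on randomised group (four levels) and the baseline value. Report the baseline-adjusted mean change and 95% CI for each cohort and for All VIT-2763, stating how the three cohorts are weighted in the latter.

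Run the model on subjects with both values observed. For indirect bilirubin, repeat it under the imputations for haemolysed samples already set out in SAP 5.1.9. Include genotype only if the smaller stratum is large enough, with the minimum size fixed before unblinding.

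The cost is one paragraph of SAP text and one extra table. The downside is the assumption of a common slope and a common residual variance across arms, which arms of 6 can hardly check. For that reason the model should support the planned summary and not replace it.
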